Data were collected on-line via a free and open iOS application, “DiagnosUs”, created by Centaur Labs as a platform for game-like image labeling competitions <https://www.centaurlabs.com/>). Between 6/22/21 and 6/27/21, Centaur Labs ran 24 ‘contests’ on our behalf, collecting >300,000 trials from 803 participants in 6 days. Each of the 24 contests consisted of 80 unique images of a skin lesion as shown in Figure 1. This is a relatively small number of images, but it kept the sessions short and encouraged participation. Images came from the International Skin Imaging Collaboration (ISIC) 2018 challenge (Codella, et al., 2019). The set contains over 1,200 melanoma images and over 7,600 nevus images.

[figure not shown]

Figure 1: Sample stimulus displays. Left: Participants are asked if a lesion is a melanoma (cancer) or a nevus (benign ‘mole’). Right: After response, if this were a feedback condition, red or green feedback would inform the observer of the correctness of the answer. In no feedback conditions, neutral feedback indicated that the response had been registered.

On each of the six days, there were four contests available. These were:

- 1) Low Prevalence – No Feedback; consisting of 20% (16) melanoma images
- 2) Low Prevalence – Feedback; prevalence was the same as in #1, but with accurate, trial by trial feedback
- 3) High Prevalence – No Feedback; consisting of 50% (40) melanoma images
- 4) High Prevalence – Feedback; prevalence was the same as in #3, but with accurate, trial by trial feedback

The contests were randomly assigned to participants with the constraint that they did not run the same type of contest more than once in a day. Participants could take part in as many or as few contests as they wished over the course of the six days and they could end up repeating a

condition from one day on another day. The prevalence and feedback conditions were not advertised to participants. Accuracy is the main dependent variable though we also collected response times.

Because of the on-line, voluntary nature of the data collection, we did not have control over the viewing conditions or the type of screen used. We compensated by collecting a very large dataset (see below).

Observers

We collected data from 803 unique individuals. For each individual, we have a crude categorization of expertise as shown in Table 1:

Medical Student	337
Pre-Med Student	174
No Medical Experience	145
Medical Doctor	54
Other Healthcare Professional	47
Nurse	25

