To analyze the effect of one block on the next block, we derived all the pairs of blocks in the dataset. For each of the blocks, we calculated the true positive and false positive proportions and used these to derive the standard signal detection measure of d' and criterion (Note that we are refraining from using the term “sensitivity” because it is used to refer to d' in the behavioral science community and to the true positive rate in the medical community.) For the primary analyses, pairs were removed from analysis if either member of the pair produced a d' of less than 0.5. The task was relatively difficult and we had little control over the motivation of participants in online study of this sort. The probability of achieving a $d' > 0.5$ by guessing through an 80 trial block is $\sim 0.6\%$. A cutoff of 0.4 would permit over 2% of blocks to be pure guessing. A $d' > 0.5$ cutoff left 2,080 pairs of blocks. The distribution of those pairs is shown in

Table 5:

		Block N				
		Low, No Feedback	Low, Feedback	High, No Feedback	High, Feedback	
Block N+1	Low, No	29	140	151	134	454
	Low, Feed	92	110	150	218	570
	High, No	261	117	51	117	546
	High, Feed	147	218	118	27	510
		529	585	470	496	2080

Table 5: Counts of the 16 different pairs of Block N and Block N+1.

As can be seen, there is a good, if uneven distribution of pairs. There are fewer pairs on the diagonal where the condition is the same in Blocks N and N+1. In order to run the same block, twice in a row, participants needed to encounter that condition last on Day K and first on Day K+1 since the same condition could not be run twice on the same day. The marginals show that this distribution of the four different conditions is very roughly uniform.

First, we compare performance in the four conditions, regardless of their position the sequence of sessions for each observer. Figure 2 shows the signal detection measures of d' and criterion, “c”. These values cannot be computed if $p(\text{True Positive}) = 1.0$ or $p(\text{False Positive}) = 0.0$. Accordingly, in keeping with one standard practice, we add $\frac{1}{2}$ of a False Positive error to each False Positive count (Hautus, Macmillan, & Creelman, 2021).

[figure not shown]

Figure 2: D' and Criterion as a function of condition. Each dot represents one of 2080 blocks of data. Black lines show mean and +/- 95% CI of the mean.

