each of these effects, we derive measures of d' and criterion for each of the 16 pairs (combinations of one of four 'first blocks' with one of four 'second blocks'). We then subtract a baseline derived from all blocks of the second block condition. We use the second blocks as the baseline because we are looking for a change in the second block. In fact, it doesn't make much difference. Many second blocks in one pair are the first blocks in a subsequent pair and the baselines would be very nearly the same if all blocks were included as in Figure 2 above. Thus, for example, to assess the influence on criterion of Low Prevalence without Feedback (Condition 1 in the figures to follow) on High Prevalence without Feedback (Cond 3), we compute $\text{Criterion}(\text{pair 13}) - \text{Criterion}(\text{Cond 3})$. This is done for each of the 2080 pairs of blocks using the $d' > 0.5$ filter. The data for each of these 2080 "good" pairs of blocks are posted on the Open Science Framework at <https://osf.io/hck5n/>.

Figure 4 shows the change in D' as a function of pair with each dot representing one pair of blocks. Statistical tests are simple T-tests against a null hypothesis of no change in d' from block 1 to block 2. Three pairs, forming no obvious pattern, reach statistical significance (all $p = \sim 0.02$, all Cohen's $d = \sim 0.2$). As these are not corrected for multiple comparisons, these should not be considered strong effects. The general picture is of little or no effect of the first block of trials on d' in the second block of trials.

[figure not shown]

Figure 4: Change in d' on block 2 as a function of the nature of block 1. X-axis gives numerical values for each member of a pair where 1 = low prevalence, no feedback, 2 = low prevalence, with feedback, 3 = high prevalence, no feedback, and 4 = high prevalence, with feedback. P-values show results for simple t-tests, testing against the null hypothesis that there is no change in d' . Black lines show means +/- 95% confidence intervals.

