A different pattern is seen in the criterion data, plotted in Figure 5. Here, there are two clear clusters of significant effects. When block 1 has low prevalence and feedback, criterion on block 2 is more conservative (Pairs where Block 1 is low prevalence with feedback, all $p < 0.006$, Cohen's d between 0.2 and 0.5). When block 1 has high prevalence and feedback, criterion on block 2 is more liberal (Pairs where Block 1 is high prevalence with feedback, $p < 0.0005$, pair

44, $p = 0.017$; note that there are only 27 pairs of this variety in the dataset, All Cohen's d between 0.2 and 0.5). When block 1 does not have feedback, there is no effect on criterion in pair 2, except, perhaps, for 'high feedback' on Block 2 ($p < 0.028$, again, not corrected for multiple comparisons, Cohen's $d = 0.18$). This is the main finding of the paper. Criterion can be manipulated by the prevalence of the preceding block of trials, but only if the participants received feedback on that first block.

[figure not shown]

Figure 5: Change in criterion on block 2 as a function of the nature of block 1. P-values
show results for simple t-tests, testing against the null hypothesis that there is no change in
criterion. Black lines show means +/- 95% confidence intervals.

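### The zero line for block-to-block criterion change is built from second blocks with a different mix of predecessors in each condition, so tests against zero carry an offset, largest when block 2 is High Feedback

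*Combined protocol and SAP*

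**What the plan says.** In the Specific Protocol, under the heading on how one block influences the next, each of the 2,080 pairs is scored as the block-2 measure minus a reference value: "We then subtract a baseline derived from all blocks of the second block condition". The reference uses second blocks. On that choice the text remarks "In fact, it doesn't make much difference", because most second blocks are also first blocks of a later pair and an all-block baseline would be almost the same. Each of the 16 cells is then t-tested against zero (Figures 4 and 5), and the scoring carries through to Figures 7 and 8.

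The Methods assign contests at random to participants on condition that "they did not run the same type of contest more than once in a day". Statistical Analysis / Results notes that same-condition pairs are therefore scarce, "since the same condition could not be run twice on the same day". It describes the spread of pairs as good though uneven.

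For criterion, the text reports conservative shifts after Low Feedback (all p < 0.006) and liberal shifts after High Feedback (p < 0.0005, except High Feedback -> High Feedback at p = 0.017 on 27 pairs), with Cohen's d between 0.2 and 0.5 throughout. After a block without feedback it reports no effect, "except, perhaps, for 'high feedback' on Block 2" (p < 0.028, d = 0.18, uncorrected). It concludes that prevalence carries over only when the first block gave feedback.

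**The concern.** The text reads zero as no influence from block 1. By construction, zero is the average influence of whatever happened to precede that block-2 condition. If Low Feedback pushes criterion one way and High Feedback the other, the two cancel in the reference only where they precede equally often. Where they do not, every cell in that row of Table 5 moves by a constant, including cells whose predecessor did nothing.

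Three readings depend on where zero lies: whether a no-feedback block has any effect, how large each feedback effect is, and whether an effect is bigger for one block-2 condition than another. The conclusion that feedback is necessary rests on the first. The remark about the choice of baseline does not settle the matter. It compares two references that share most of their blocks, and says nothing about the mix of predecessors inside either.

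**Working it through.** **Inputs.** Table 5 rows (block 2), columns in the order Low No Feedback, Low Feedback, High No Feedback, High Feedback, total: the High-Feedback row is "High, Feed 147 218 118 27 510", the Low-Feedback row is "Low, Feed 92 110 150 218 570", and the column totals are "529 585 470 496 2080". The p-values and d values come from the text around Figure 5. Two-sided 0.05 is assumed, since no alpha is stated.

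**1. Table 5 reproduces.** Row totals are 454, 570, 546 and 510. They sum to 2,080, as do the column totals.

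**2. Predecessor imbalance by row.** This is the share after Low Feedback minus the share after High Feedback.

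| Block 2 | After Low Feedback | After High Feedback | Difference |
|---|---|---|---|
| Low No Feedback | 140/454 = 30.8% | 134/454 = 29.5% | +0.013 |
| Low Feedback | 110/570 = 19.3% | 218/570 = 38.2% | -0.189 |
| High No Feedback | 117/546 = 21.4% | 117/546 = 21.4% | 0 |
| High Feedback | 218/510 = 42.7% | 27/510 = 5.3% | +0.375 |

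**3. Source of the imbalance.** The repeat rule accounts for the 5%. An even split of the other 510 - 27 = 483 High-Feedback pairs would put 161 (31.6%) after Low Feedback, against 218 observed. The rule alone would give (161 - 27)/510 = 0.263 of the 0.375. The rest is uneven ordering.

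**4. Effect on the cells.** Assume additive shifts of +delta after Low Feedback, -delta after High Feedback and 0 after no feedback. A cell then reads its own shift minus delta times the difference in step 2.

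- Before High Feedback: a no-effect predecessor reads -0.375 delta, Low Feedback reads 1 - 0.375 = +0.625 delta, and High Feedback reads -1 - 0.375 = -1.375 delta.
- Before Low Feedback: a no-effect predecessor reads +0.189 delta.
- Before either no-feedback condition: the offset is about 0.

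**5. Size of delta.** The reported d values of 0.2 to 0.5 already have the baseline subtracted, so they are not delta. In the High-Feedback row, Low Feedback -> High Feedback of at least 0.2 needs delta of at least 0.2/0.625 = 0.32. High Feedback -> High Feedback of at most 0.5 needs delta of at most 0.5/1.375 = 0.36. That cell's p = 0.017 at n = 27 corresponds to d = 0.49, hence delta = 0.49/1.375 = 0.36. The offset for a no-effect predecessor is then 0.375 x 0.32 = 0.12 to 0.375 x 0.36 = 0.135 SD, in the liberal direction. With n = 147, such a cell would reach p < 0.05 about 30% to 36% of the time.

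**6. Which cell is the exception.** With t = d x sqrt(n), d = 0.18 gives p = 0.031 at n = 147 (0.026 to 0.036 over the rounding of d) and p = 0.053 at n = 118 (0.047 to 0.060). The reported p < 0.028 fits Low No Feedback -> High Feedback.

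**7. Its direction.** The text does not give the sign. Deviations from a row mean sum to zero. Assuming a common SD and a baseline equal to that mean, with +0.2 on 218 pairs and -0.49 on 27, the 147 + 118 = 265 no-feedback pairs must average -(43.6 - 13.2)/265 = -0.115 SD. If the exception is -0.18, the other no-feedback cell is about -0.03. If it were +0.18, the other would be about -0.48, or t = 0.48 x sqrt(118), about 5.2, which could not have gone unreported. The exception is therefore liberal, as the offset predicts.

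**The case against.** The strongest reply is that the baseline cancels whenever two predecessors of the same block-2 condition are compared, and the main finding is such a comparison in substance: conservative after Low Feedback, liberal after High Feedback. That stands.

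Several stronger readings are tempting, and the documents do not support them.

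- **The offset could reach 0.19 SD.** That takes delta = 0.5, which makes High Feedback -> High Feedback 0.69 SD and p = 0.0014 at n = 27, against the reported 0.017. At the other end, delta = 0.2 makes Low Feedback -> High Feedback 0.125 SD and p = 0.066 at n = 218, against the reported p < 0.006.
- **The offset fully explains the exception.** The reported 0.18 lies above 0.12 to 0.14. The gap of about 0.05 is within one standard error (1/sqrt(147) = 0.08), so it is not evidence of a real effect either. The false-positive change in the same pair has p = 0.001, or d of about 0.28 at n = 147, which is more than the criterion offset would give if the two scales behave alike.
- **The offset explains why Low Feedback -> High Feedback fails for true positives.** The reported p = 0.38 is t = 0.88. Undoing the shrinkage gives 0.88/0.625 = 1.41, p = 0.16, still not significant.
- **The exception is presented as a finding.** The text hedges it and does not adopt it; removing it would support the stated conclusion.
- **The repeat rule caused the whole imbalance.** Step 3 shows otherwise, and 110 Low-Feedback repeats arose under the same rule.

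It is also fair to say that the predicted conservative offset before Low Feedback has no reported counterpart. At 0.189 x 0.32 to 0.36, it is only 0.06 to 0.07 SD.

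**Conclusion.** The concern holds for everything measured against zero: the one-sample t-tests, the reading of the no-feedback cells, and comparisons of baseline-subtracted cells across block-2 conditions. The offset is about 0.12 to 0.14 SD liberal when block 2 is High Feedback, about half that and conservative when block 2 is Low Feedback, and negligible otherwise. It is enough to account for much of the single no-feedback exception, though not demonstrably all of it.

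A reader might infer that the main finding is an artefact, or that no cells can be compared. Neither follows, because contrasts within a block-2 condition are unaffected and the direction of the finding survives.

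The size rests on additive, equal and opposite feedback shifts, no carry-over from no-feedback blocks, and a common SD. The documents print none of the underlying cell means. If no predecessor had any effect there would be no offset, but the documents report that feedback blocks do.

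**What to change.** 1. **Primary test.** Replace the t-tests against zero with contrasts between predecessors within each block-2 condition, for example Low Feedback and High Feedback each against the pooled no-feedback predecessors. The baseline then cancels. Contrast the two no-feedback predecessors with each other as well; this tests directly whether prevalence carries over without feedback.
2. **Zero line in Figures 4, 5, 7 and 8, if kept.** Use the equally weighted mean of the four predecessor means within each block-2 condition. With shifts of size a after Low Feedback and b after High Feedback, the offset becomes (a - b)/4 in every row, so rows are comparable. It vanishes only if a = b, and that limit should be stated.
3. **Sensitivity check only.** Use participants' first-ever blocks as an unexposed reference. They differ in practice, and in selection, since many participants ran only one block.
4. **Text.** Limit the remark "In fact, it doesn't make much difference" to what it compares, second-block with all-block baselines, and report the sign of the exception.

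**Cost.** This is re-computation on posted data, with some loss of precision. In SD units and treating pairs as independent, equal weighting raises the High-Feedback baseline SE from 1/sqrt(510) = 0.044 to sqrt[(1/147 + 1/218 + 1/118 + 1/27)/16] = 0.060, about a third, because of the 27-pair cell. In the same row, the Low-Feedback contrast against pooled no-feedback has SE sqrt(1/218 + 1/265) = 0.091, against 0.068 for the present test. For High Feedback it is sqrt(1/27 + 1/265) = 0.202, against 0.192.

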A one-way ANOVA shows a main effect of condition on d' ($F(3, 2076) = 6.461, p = 0.0002$, partial eta-sq = 0.01) and Šídák's multiple comparisons test shows that performance on skin cancer detection task is modestly better in the high prevalence, feedback condition than in the high prevalence, no-feedback condition ($p = 0.008$). Prevalence effects are better understood as criterion shifts. An ANOVA shows a very large main effect of condition on criterion ($F(3, 2076) = 30.16, p < 0.0001$, partial eta-sq = 0.04). Pairwise comparisons show a strong LPE effect when feedback is given ($p < 0.0001$). Criterion becomes more conservative at low prevalence. Without

feedback, criterion becomes slightly more liberal on average (0.34 to 0.31). This is not statistically significant ($p = 0.47$). As noted earlier, the PICC effect (Levari, et al., 2018), while certainly real, is typically more fragile than the LPE effect in the opposite direction (Lyu, et al., 2021). The differences between conditions with feedback and without feedback are highly significant ($p < 0.0001$ for each comparison). A significant LPE effect is seen if analysis is restricted to each participant's first block of data ($p < 0.0001$). There is no PICC effect. If all blocks of data are used, eliminating the $d' > 0.5$ filter, there is, again a significant LPE ($p < 0.0001$) and an insignificant PICC effect ($p = 0.1244$).

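### The carry-over tests compare block 2 with its own condition mean, but the stated null is a change from block 1 (d') or a change with no named reference (figure captions)

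*Combined protocol and SAP*

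**What the plan says.** The Specific Protocol, section on how one block influences the next, defines the score for each pair of blocks: "We then subtract a baseline derived from all blocks of the second block condition". Its worked example, for the influence of condition 1 on condition 3, is the criterion of pair 13 less the criterion of condition 3. The paragraph on d' that follows gives the hypothesis as "Statistical tests are simple T-tests against a null hypothesis of no change in d' from block 1 to block 2".

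For criterion, the Figure 5 caption reads "Change in criterion on block 2 as a function of the nature of block 1". The captions of Figures 4 and 5 both describe their p-values as "testing against the null hypothesis that there is no change in" the measure, without naming what the change is measured from. Figures 6 to 8 keep the change label.

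Under Statistical Analysis / Results, the ordinary effect of condition on criterion is given: "Pairwise comparisons show a strong LPE effect when feedback is given ($p < 0.0001$). Criterion becomes more conservative at low prevalence". The carry-over section then reports a conservative shift in block 2 after Low Feedback and a liberal shift after High Feedback, with Cohen's d between 0.2 and 0.5 in each cluster, and presents this as the main finding.

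**The concern.** The hypothesis in the d' sentence is not the one the t-test addresses. A null of no change from block 1 to block 2 needs the block 1 score, and the formula does not contain it. Nor would that null express absence of carry-over: when two blocks differ in condition, scores move between them through the condition effect alone.

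The quantities can differ in sign. With feedback, criterion is more conservative at low prevalence, so a person going from Low Feedback to High Feedback is expected to become more liberal. The document reports a conservative shift for that pair. Both can be true, because one is relative to the person's own block 1 and the other to the average High Feedback second block. Someone who reuses the posted pair-level data under the stated null would compute a different quantity.

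There is also a precision cost. Stable differences between people in response bias stay in every score as error, although block 1 carries information about them.

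**Working it through.** **Inputs.** Table 5 and its text: "A $d' > 0.5$ cutoff left 2,080 pairs of blocks", with 218 pairs Low Feedback to High Feedback and 218 in reverse. Condition effect on criterion: F(3, 2076) = 30.16, partial eta-squared 0.04. No-feedback mean criteria: 0.34 (high prevalence) and 0.31 (low), p = 0.47. Each feedback versus no-feedback difference: p < 0.0001. Cohen's d is given as a range over each cluster, not for each pair.

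**Reproducing the plan's figure.** Partial eta-squared = 3F/(3F + 2076) = 90.48/2166.48 = 0.0418, which agrees with 0.04.

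**Share of pairs.** 218 + 218 = 436; 436/2,080 = 21%.

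**Gap between the feedback conditions.** Cohen's f = √(90.48/2076) = 0.209. Suppose equal group sizes, and feedback means at m + x and m − x around two equal no-feedback means m. Then f = x/√2, so x = 0.295 SD and the gap is 0.59 SD. A search over feedback means that satisfy the F value, the 0.31 and 0.34 means and the stated p-values, using either set of Table 5 margins, gives 0.55 to 0.58 SD. One corner solution gives 0.24 to 0.25 SD. It needs the Block N margins, all p-values unadjusted, and both feedback means on the same side of the no-feedback means.

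**Implied within-person change in criterion.** Assume block 1 sits on average at its condition mean, and that the SD behind Cohen's d is close to the within-condition SD. For Low Feedback to High Feedback, block 2 minus block 1 = shift − gap. The reverse pair mirrors this.

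| Gap (SD) | Shift +0.2 | Shift +0.5 |
|---|---|---|
| 0.59 | −0.39 | −0.09 |
| 0.58 | −0.38 | −0.08 |
| 0.55 | −0.35 | −0.05 |
| 0.25 | −0.05 | +0.25 |

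**Where the shifts lie.** With n = 218, p < 0.006 implies d of at least 0.19 for Low Feedback to High Feedback, and p < 0.0005 implies at least 0.24 for the reverse. If the baseline is the mean of the filtered second blocks, the deviations within a block 2 condition sum to zero. Taking a common SD, d = −0.49 for the 27 High Feedback repeats (from p = 0.017), d = −0.18 for the 147 Low No Feedback to High Feedback pairs (sign assumed) and d = 0.2 for the 218, the other 118 must average −(43.6 − 13.2 − 26.5)/118 = −0.03. So a shift near 0.2 fits the first pair type. In the corner solution the reverse pair, at 0.24 or more, would show a within-person change near zero or of the same sign as reported.

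**d'.** F = 6.461 gives partial eta-squared 19.383/(19.383 + 2076) = 0.009. The text does not name the three pairs that reach significance, so no comparison of signs can be made.

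**Covariate.** With within-person correlation r, adjustment removes r² of the residual variance. For r = 0.3 to 0.6 (assumed) that is 9% to 36%; the standard error is multiplied by √(1 − r²) = 0.95 to 0.80.

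**The case against.** A reader might infer that the main result points the wrong way, or that the criterion endpoint itself is described as a change from block 1 to block 2. The documents support neither. That phrase is attached to d' only; the criterion text and captions speak of criterion on block 2. The baseline and formula are disclosed just before the tests, with a reason. The question is whether block 1 influences block 2, and a raw difference between the blocks would mix in the ordinary condition effect. Deviation from the block 2 condition mean, grouped by preceding condition, is a sensible answer, and its reported direction stands.

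The sign argument is also narrow: one measure, 2 of 16 pair types, and feedback means that appear only in a figure not shown.

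Against the covariate, block 1 is measured during the exposure being studied, so it is not a clean baseline; the correlation is assumed; and the main effects are already significant.

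All of this limits the point without removing it. Disclosing the formula does not correct the hypothesis stated after it, and the captions leave the reference unnamed. The document's remark that the baseline choice matters little concerns second blocks versus all blocks of a condition, not the person's own block 1. Centring by condition answers the exposure objection as far as the average block 1 effect goes.

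**Conclusion.** The null for d' is wrongly stated, and the no-change wording in the captions of Figures 4 and 5 is incomplete. This follows from the text alone and needs no assumption. The contrast is fit for its purpose and its reported direction is not in doubt.

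The practical size is that, for criterion, 21% of pairs probably have a within-person change opposite in sign to the reported deviation. That rests on a feedback gap of about 0.55 to 0.59 SD and on the block 1 and SD assumptions above; with a gap near 0.25 SD it holds only for shifts below about 0.25 SD. Nothing comparable is shown for d'. The precision gain from using block 1 is plausible, but its size depends on an assumed correlation.

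**What to change.** In the section on how one block influences the next, state the null for both d' and criterion as: the mean block 2 score, given the preceding condition, equals the mean for that block 2 condition. Label Figures 4 to 8 as deviation from the second-block condition mean.

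Add the person's block 1 criterion (or d') as a covariate, centred on the mean of its block 1 condition. Without that centring the covariate would absorb part of the carry-over effect under test. State that centring improves precision only: it does not correct average differences between the groups of people behind different block 1 conditions.

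The cost is rewording, new figure labels and one reanalysis with a variable already in hand. No new data are needed.

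### The conclusion that block 1 has little or no effect on d' rests on 16 separate cell tests, mostly underpowered at 0.2 SD, with no pooled estimate and no margin

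*Combined protocol and SAP*

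**What the plan says.** In the Specific Protocol, under the heading on how one block influences the next, "we derive measures of d' and criterion for each of the 16 pairs". Each block 2 value has the mean of all second blocks of its condition subtracted. For d', "Statistical tests are simple T-tests against a null hypothesis of no change in" d'. The outcome is reported as "Three pairs, forming no obvious pattern, reach statistical significance", each with p of about 0.02 and Cohen's d of about 0.2. These are then set aside: "As these are not corrected for multiple comparisons, these should not be considered strong effects". The conclusion follows: "The general picture is of little or no effect of the first block of trials on" d'.

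The next paragraph contrasts this with criterion ("A different pattern is seen in the criterion data, plotted in Figure 5"). There, two clusters of effects with Cohen's d between 0.2 and 0.5 are named as the paper's main finding.

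The cell sizes are in Table 5 ("Counts of the 16 different pairs of Block N and Block N+1"). The Figure 4 caption says that means with 95% confidence intervals are plotted for each pair. The earlier ANOVA on d' tests the condition of the current block, not of the preceding one.

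**The concern.** A null is drawn from many small tests, most of which did not reach significance. That supports a statement of little effect only if the tests could have seen an effect that matters, or if an interval rules one out. The text gives no power, no detectable effect, no margin and no pooled estimate of the effect of the preceding block. The same 16-cell approach can display a strong, consistent pattern, as it does for criterion, and still be too coarse to exclude a modest one.

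At stake is the contrast between criterion, which moves, and d', which is said to move little or not at all. A modest d' effect is plausible on the document's own account: it finds d' higher with feedback than without at high prevalence (p = 0.008), and it likens carry-over to education rather than adaptation.

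**Working it through.** **Inputs.** Table 5 counts, with rows for block 2 condition and columns for block 1 condition, both in the order Low-No, Low-Feedback, High-No, High-Feedback:

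- Low-No: 29, 140, 151, 134
- Low-Feedback: 92, 110, 150, 218
- High-No: 261, 117, 51, 117
- High-Feedback: 147, 218, 118, 27

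The total is 2,080. Assumptions: two-sided 5% (implied but not stated), unit SD, and independent blocks unless a design effect is given.

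**Reproducing the reported figures.** For a one-sample test, t = d√n. With d = 0.2, n = 134 gives t = 2.32 and p = 0.022; n = 151 gives t = 2.46 and p = 0.015. This matches p of about 0.02 with d of about 0.2. For criterion pair 44 (n = 27, p = 0.017) the same form gives d = 0.49, inside the stated 0.2 to 0.5.

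**Power per cell at 0.2 SD from baseline** (noncentral t, noncentrality 0.2√n):

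| n | Power |
|---|---|
| 27, 29, 51 | 17%, 18%, 29% |
| 92, 110 | 48%, 55% |
| 117 (twice), 118 | 57%, 57%, 58% |
| 134, 140, 147 | 63%, 65%, 67% |
| 150, 151 | 68%, 68% |
| 218 (twice), 261 | 84%, 84%, 90% |

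Thirteen of 16 cells are below 80%, and the mean is 0.58. Reaching 80% needs n = 199. The 95% interval half-width runs from 0.12 SD (n = 261) to 0.40 SD (n = 27).

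**Two scales.** The document's Cohen's d is a deviation from a baseline that contains the cell itself. Suppose feedback-first pairs have d' higher by Δ than no-feedback-first pairs, and let f be the feedback-first share of a row. Feedback-first cells then sit at +Δ(1 − f) and the others at −Δf. From Table 5, f = 274/454 = 0.60, 328/570 = 0.58, 234/546 = 0.43 and 245/510 = 0.48. With Δ = 0.2 SD, each cell lies only 0.08 to 0.12 SD from baseline.

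**Simulating the stated procedure** (16 tests, self-including baseline, Table 5 counts):

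- Δ = 0.2 SD (about 0.1 SD from baseline): about 2.7 significant cells on average; three or fewer in about 70% of datasets.
- Δ = 0.15 SD: three or fewer in 92%.
- Δ = 0.4 SD (about 0.2 SD from baseline): about 9 significant cells; three or fewer in under 0.1%.

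**Pooled contrast.** Let a be the feedback-first and b the no-feedback-first pairs within each block 2 condition. The information is the sum of ab/(a + b):

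(274×180)/454 + (328×242)/570 + (234×312)/546 + (245×265)/510 = 108.6 + 139.3 + 133.7 + 127.3 = 508.9

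SE = 1/√508.9 = 0.044 SD. For Δ = 0.2 SD, 0.2/0.0443 = 4.51, and power is Φ(4.51 − 1.96), about 99%. Multiplying the variance by an assumed design effect of 2 gives SE 0.063 and power 89%; a design effect of 3 gives SE 0.077 and 74%. The documents give no within-participant correlation, so this range is an assumption.

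**The case against.** The strongest reply is that the document judges by pattern, not by a count of significant cells, and that its hedged wording already allows a small effect. Much of this stands. A d' effect as large as the smallest accepted criterion effect (0.2 SD from baseline) would have produced about nine significant cells and could hardly have been missed. Isolated small effects are also discounted for criterion, so the standard is applied evenly.

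Several stronger readings are tempting, and the documents do not support them:

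- **That all 16 tests were non-significant, or that the cells could detect nothing.** Three reached p of about 0.02, and 12 of 16 cells have more than 50% power at 0.2 SD.
- **That no confidence bounds exist.** The Figure 4 caption says they are plotted by cell. What is missing is a pooled interval.
- **That three significant cells exceed chance and so point to a real effect.** With independent tests, three or more of 16 at p < 0.05 has probability 4.3%. But participants contributed up to 24 blocks, and at an assumed design effect of 2 a null simulation gives 24%. A stricter cutoff such as 0.025 would be chosen after seeing the p-values.
- **That a real 0.2 SD between-group effect would usually leave the same scattered picture.** In simulations with exactly three significant cells, all three had the feedback-consistent sign about 99% of the time. The reported lack of pattern therefore counts informally against such an effect. It is not an estimate, though, and the text does not name the three pairs or their directions.
- **That the main finding falls.** The criterion result does not need a null on d'.

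**Conclusion.** The concern holds in a limited form. The cell-by-cell analysis makes a feedback-first d' effect of 0.2 SD or more from baseline implausible. It does not exclude one of about 0.1 SD from baseline, or 0.2 SD between feedback-first and no-feedback-first pairs. With no margin stated, a reader cannot tell whether an effect of that size counts as little. A pooled contrast on the same 2,080 pairs would address it directly, with about 99% power if blocks are independent and 89% or 74% at design effects of 2 or 3.

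These figures rest on a two-sided 5% level, unit SD and the assumed design effects. This is a gap in how a secondary null is supported and worded, not an error in the criterion analysis.

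**What to change.** Add one model of block 2 d' on block 2 condition plus block 1 condition, with participant-clustered standard errors. Report:

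- the 3-df test of block 1 condition;
- the feedback-first minus no-feedback-first contrast, with its 95% confidence interval;
- the Low-Feedback-first minus High-Feedback-first contrast, with its 95% confidence interval.

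Word the conclusion by the largest effect that those intervals exclude, and say whether the scale is a between-group difference or a deviation from baseline, since the first is roughly twice the second here. The contrasts should carry the conclusion. For a 0.2 SD shift after one block 1 condition only, the 3-df test has 89% to 94% power if blocks are independent but 58% to 66% at a design effect of 2.

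The cost is one extra analysis on data already posted and a reworded sentence. The d' null may have to be stated less strongly; if the intervals are tight around zero, it becomes better supported than it is now.
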